8 STATISTICAL CONSIDERATIONS

8.1 Sample Size Determination

The sample size calculation is driven by the power to compare the proportion of subjects who achieve ACR70 response at Week 12 between each BMS-986142 dose arm and placebo arm. The target population consists of mixed subjects who are MTX-IR ($\geq 70\%$) and TNF-IR ($\leq 30\%$). For co-primary endpoint of ACR70 at Week 12, 82 subjects per arm will provide ~ 90% power to detect a treatment difference of 17% at the type I error rate of $\alpha = 0.05$ (two-sided), assuming the placebo response rate of 2.5%. The assumed treatment difference of 17% is about double of median difference observed from historical data on approved drugs across different mechanism of actions (MOAs).

If the placebo response rate in ACR70 at Week 12 is higher than planned 2.5% (eg, 5%), 82 subjects per arm can still provide 84% power to detect a difference of 17%.

For the population of MTX-IR ($\geq 70\%$), 57 subjects per arm will provide 78% power to detect a treatment difference of 18% in ACR70 at the Type 1 error rate of $\alpha = 0.05$ (two-sided), assuming the placebo response rate is 2.5%.

For the other co-primary endpoint of ACR20 at Week 12, 82 subjects per arm will provide >99% power to detect a difference of 34% over placebo at the type I error rate of $\alpha = 0.05$ (two-sided), assuming placebo response rate of 33%. The assumed treatment difference of 34% and

placebo response rate of 33% were based on the observed data from approved drugs across different MOAs.

For the population of MTX-IR ($\geq 70\%$), 57 subjects per arm will provide 95% power to detect a treatment difference of 35% in ACR20 at the Type 1 error rate of $\alpha = 0.05$ (two-sided), assuming the placebo response rate is 40%.

An interim analysis (IA) will be conducted when about 20 subjects reach week 4 (complete 4 weeks of treatment or discontinue). Based on the totality of efficacy, safety, and PK at Week 4 IA, the following adaptation(s) may be recommended:

- Stop ineffective or unsafe dose(s)
- Introduce new dose(s) arms if needed and enroll (up to about 82 subjects per arm)
- Complete full enrolment for all efficacious arms (up to about 82 subjects per arm)
- Stop the study enrollment if all dose arms are stopped for safety or futility;

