8.5 Interim Analyses

After about 20 subjects per treatment arm have completed at least 4 weeks of the treatment period or discontinued the treatment, an interim analysis will be conducted to assess the efficacy of the BMS-986142 dose arms and the overall safety. The interim analysis will use pre-specified efficacy, safety and PK endpoints. The results of the interim analysis will be reviewed by an unblinded sponsor team who is not involved in the study conduct and who will provide recommendations with regard to the adaptive design decisions to the blinded study team.

Efficacy analysis (DAS28) using Bayesian modeling and dose/exposure response analysis:

The interim analysis will be performed on all available data of DAS28 change from baseline up to Week 12 using a Bayesian predictive approach.²³ This analysis assumes that the DAS28 at Week 4 and at Week 12 in the subjects who have not yet been observed will be similar to what was observed for the subjects included at Week 4 and Week 12, respectively. As such the unobserved data will be simulated from the predictive distribution conditional on the interim data and the prior distribution of the treatment difference (using a non-informative prior). Under the Bayesian framework, the posterior distribution of the treatment difference (BMS-986142 active

dose – Placebo) will be constructed to determine the predictive probability of $\Delta\Delta$ DAS28 improvement greater than a cutoff value at the planned end of the trial for each dose arm.

Note: $\Delta\Delta$ DAS28 improvement: The difference of change from baseline in DAS28-CRP between active dose arm and placebo arm. The lower is DAS28 score, the better is the disease status.

The Bayesian predicative analysis and the dose/exposure response analysis will be used to facilitate decision-making if new BMS-986142 dose(s) will be needed to fully characterize dose-efficacy relationship. Pre-specified efficacy endpoint (DAS28) will be assessed with exposure endpoints to guide the selection of new dose levels in different scenarios as described below. Considering the safety margin estimated from non-clinical studies, new dose levels based on the interim analysis will not be greater than 350 mg/day.

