5 SAMPLE SIZE AND POWER

The sample size calculation is driven by the power to compare the proportion of subjects who achieve ACR70 response at Week 12 between each BMS-986142 dose arm and placebo arm without multiplicity adjustment. The target population consists of mixed subjects who are TNF-IR ($\geq 80\%$) and MTX-IR ($\leq 20\%$). For co-primary endpoint of ACR70 at Week 12, 82 subjects per arm will provide $\sim 80\%$ power to detect a treatment difference of 14% at the type I error rate of $\alpha = 0.05$ (two-sided), assuming the placebo response rate of 2.5%. The assumed treatment difference of 14% is double of 7% that was median difference observed from historical data on approved drugs across different mechanism of actions (MOAs).

If the placebo response rate in ACR70 at Week 12 is higher than planned 2.5% (eg, 5%), 82 subjects per arm can still provide $> 70\%$ power to detect a difference of 14%.

For the population of TNF-IR ($\geq 80\%$), 65 subjects per arm will provide 68% power to detect a treatment difference of 14% in ACR70 at the Type 1 error rate of $\alpha = 0.05$ (two-sided), assuming the placebo response rate is 2.5%.

For the other co-primary endpoint of ACR20 at Week 12, 82 subjects per arm will provide 98% power to detect a difference of 31% over placebo at the type I error rate of $\alpha = 0.05$ (two-sided), assuming placebo response rate of 22%. The assumed treatment difference of 31% and placebo response rate of 22% were based on the observed data from approved drugs across different MOAs.

For the population of TNF-IR ($\geq 80\%$), 65 subjects per arm will provide 94% power to detect a treatment difference of 30% in ACR20 at the Type 1 error rate of $\alpha = 0.05$ (two-sided), assuming the placebo response rate is 18%.

An interim analysis (IA) will be conducted when about 20 subjects reach week 4 (complete 4 weeks of treatment or discontinue). Based on the totality of efficacy, safety, and PK at Week 4 IA, the following adaptation(s) may be recommended:

- Stop ineffectual or unsafe dose(s)
- Introduce new dose(s) arms if needed and enroll (up to about 82 subjects per arm)
- Complete full enrollment for all effective arms (up to about 82 subjects per arm)

- Stop the study enrollment if all dose arms are stopped for safety or futility;

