7.9 Interim Analyses

After about 20 subjects per treatment arm have completed at least 4 weeks of the treatment period or discontinued the treatment, an interim analysis will be conducted to assess the efficacy of the BMS-986142 dose arms and the overall safety. The interim analysis will use pre-specified efficacy, safety and PK endpoints. The results of the interim analysis will be reviewed by an unblinded sponsor team who is not involved in the study conduct and who will provide recommendations with regard to the adaptive design decisions to the blinded study team.

Population PK and exposure-response analysis may be performed to support the statistical Bayesian analysis and to facilitate decisions around dose selection. Population PK analysis to characterize the PK of BMS-986142 may be performed by pooling data from the present study with the Phase 1 study IMXXXXXX, in order to supplement the PK data as well as test for covariate effects, including but not limited to demographics, disease state, concomitant medications, etc. Exposure-response analysis may be performed using DAS28-CRP as the primary endpoint to characterize the relationship between measures of BMS-986142 exposure and reduction in DAS28-CRP. Details regarding the data evaluation and modeling methodology for interim analysis will be provided in a separate modeling and simulation analysis plan.

Efficacy analysis (DAS28) using Bayesian modeling and dose/exposure response analysis:

The interim analysis will be performed on all available data of DAS28 change from baseline up to Week 12 using a Bayesian predictive approach.¹³ This analysis assumes that the DAS28 at Week 4 and at Week 12 in the subjects who have not yet been observed will be similar to what was observed for the subjects included at Week 4 and Week 12, respectively. As such the unobserved data will be simulated from the predictive distribution conditional on the interim data and the prior distribution of the treatment difference (using a non-informative prior). Under the Bayesian framework, the posterior distribution of the treatment difference (BMS-986142 active dose – Placebo) will be constructed to determine the predictive probability of $\Delta\Delta\text{DAS28}$ improvement greater than a cutoff value at the planned end of the trial for each dose arm.

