If the predictive probability of $\Delta\Delta\text{DAS28}$ improvement being greater than 0.6 is lower than 20% in all active treatment arms, BMS team may recommend stopping further enrollment and continuing those subjects receiving therapy up to 12 weeks.

Descriptive efficacy analysis (other efficacy endpoints):

In addition to Bayesian predictive analysis above, the following as-observed clinical data up to database lock will be summarized at the time of Week 4 interim analysis to facilitate decision-making.

- ACR20/50/70 response over time
- DAS28-CRP < 2.6 , DAS28-ESR < 2.6 , CDAI ≤ 2.8 , SDAI ≤ 3.3 and Boolean remission over time
- Change from baseline in DAS28-CRP, DAS28-ESR, CDAI, SDAI over time.

Descriptive safety analysis:

For the following pre-specified safety endpoints:

- AE/SAE (including but not limited to hypertension, diarrhea, neutropenia)
- Change from baseline in vitals including systolic blood pressure (SBP) and diastolic blood pressure (DBP).

The study will be stopped if intolerable safety events are identified in all treatment arms. If intolerable safety events are identified in 1 or 2 treatment arms, these arms will be dropped and

the study will be continued with caution. New dose levels may be added based on the exposure response analysis (not greater than 350 mg daily). If intolerable safety events show a clear relationship with higher exposure of BMS-986142, a lower dose will be selected where the predicted exposure in ~ 90% of subjects does not exceed the exposure ranges associated with safety findings.

Based on the totality of safety and efficacy considerations, unsafe dose arm will be stopped immediately. The dose arm(s) that are projected to be ineffective will continue till the end of double-blind period for subjects already taking at least one dose of study medication and no new subjects will be enrolled into ineffective dose arm(s).

[REDACTED]

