8.5 Missing Measurements

8.5.1 *Imputation of Missing Data for Binary Variables*

This imputation is applicable for all binary variables (ACR20/50/70, DAS28-CRP <2.6, DAS28-ESR <2.6, and remission status defined by CDAI, SDAI and Boolean definition).

If the response cannot be assessed due to missing data or a subject's early discontinuation, the following conventions will be implemented in a sequence:

- Any subject who prematurely discontinues the trial during the double-blind period after receiving study medication will have data imputed as non-responder at all scheduled protocol visits subsequent to the point of discontinuation up to the end of the double-blind period.
- After any imputation above or none, if for some reason the binary variable still can't be determined, including the case where baseline data is missing, then its value will be set to non-responder.

For listings, missing responses will be presented as missing.

8.5.2 *Imputation of Missing Data for Continuous Variables*

For the analysis of changes from baseline values (e.g., individual components of ACR, DAS28-CRP, and DAS28-ESR etc), missing values will be dealt with via the longitudinal repeated measures analysis assuming MAR (missingness at random).

For all safety (including laboratory measurements), and PK measures, missing values will not be imputed.

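### The interim ACR and remission summaries are as-observed while the final analysis scores early stoppers as non-responders, so an arm with more early stops looks better at the interim than under the final rule

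*SAP*

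**What the plan says.** **Interim, supportive endpoints.** SAP 7.9 lists ACR20/50/70, the remission criteria and change scores, and says that "the following as-observed clinical data up to database lock will be summarized at the time of Week 4 interim analysis to facilitate decision-making". Protocol 8.5 has the same list without the as-observed label. Both documents say that final futility takes these other endpoints into account. Protocol 8.5 also makes continued enrolment into the lower dose arms depend partly on efficacy endpoints beyond DAS28; SAP 7.9 instead closes those arms to new subjects.

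**Interim, DAS28.** The 1.0 and 0.6 cut-offs apply to a Bayesian predictive analysis of all available DAS28 change data up to Week 12. It assumes that values "in the subjects who have not yet been observed will be similar to what was observed for the subjects included at Week 4" and at Week 12, respectively. Neither document says how subjects who have already stopped enter this model.

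**Trigger.** Protocol 8.5 and SAP 7.9 time the interim for when about 20 subjects per arm "have completed at least 4 weeks of the treatment period or discontinued the treatment". The protocol synopsis, Protocol 3.1 and SAP 2.1 add that the specified efficacy, safety and PK assessments are completed.

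**Final analysis.** For binary endpoints, SAP 8.5.1 says that a subject who stops prematurely "will have data imputed as non-responder at all scheduled protocol visits subsequent to the point of discontinuation", and any response still undetermined is set to non-responder. For continuous endpoints, including DAS28 change, SAP 8.5.2 uses a repeated-measures model under missing at random (MAR).

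**Visit windows.** SAP 8.7 assigns efficacy assessments by study day: Days 8-21 for D15 and Days 22-43 for D29.

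**The concern.** The interim and final analyses use the same binary endpoints with different denominators. At the interim, the ACR and remission rates describe subjects who have an assessment in the window. At the end, they describe everyone treated in the efficacy population. Under the trigger wording of Protocol 8.5 and SAP 7.9, an early stopper helps to bring the interim about and yet may be absent from its response rates.

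At stake is the quality of dose selection. A dose with more early stops can show a response rate that the final rule will not reproduce, and this could weigh in the decision to keep it enrolling. The final co-primary tests are not biased by this, because they already use non-responder scoring.

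**Working it through.** **1. The plan's own figures.** The protocol states "82 subjects per arm will provide ~ 90% power to detect a treatment difference of 17" points on ACR70, "assuming the placebo response rate of 2.5" percent. The usual two-proportion formula with continuity correction is

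power = Φ{[d − 1/n − 1.96·√(2p̄(1−p̄)/n)] / √[(p1(1−p1) + p0(1−p0))/n]}.

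With n = 82, p1 = 0.195, p0 = 0.025 and p̄ = 0.11, this is Φ{(0.170 − 0.0122 − 0.0958)/0.0470} = Φ(1.32) = 90.6%, as stated. The SAP's "82 subjects per arm will provide $\sim 80\%$ power to detect a treatment difference of 14" points gives 80.4%, also as stated. Neither calculation includes a dropout allowance, and neither document gives a dropout rate.

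**2. Who leaves the Week 4 denominator.** An Early Termination (ET) assessment before Day 22 falls outside the D29 window, and one before Day 8 falls in no post-baseline window. Such a subject has no as-observed Week 4 response unless assessed again within Days 22-43. Under SAP 8.5.1 the same subject is a non-responder at Week 4 and at every later visit.

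**3. Size of the gap.** Let r be the response rate among subjects with data and d the proportion who stop without data in the window. The as-observed rate is r and the non-responder rate is r(1 − d). The as-observed treatment difference is larger by r1·d1 − r0·d0.

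Inputs: ACR20 of 67% (33% + 34 points) against 33%, and ACR70 of 19.5% against 2.5%, from Protocol 8.1. These are Week 12 planning rates, taken here as completer rates. The dropout rates are assumed.

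| Dropout, active / placebo | ACR20 as observed | ACR20 non-responder | ACR70 as observed | ACR70 non-responder |
|---|---|---|---|---|
| 10% / 5% | 34.0 | 29.0 | 17.0 | 15.2 |
| 20% / 5% | 34.0 | 22.3 | 17.0 | 13.2 |
| 30% / 5% | 34.0 | 15.5 | 17.0 | 11.3 |
| 10% / 10% | 34.0 | 30.6 | 17.0 | 15.3 |

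For example, at 20% / 5%, 0.67 × 0.80 − 0.33 × 0.95 = 0.536 − 0.3135 = 0.2225. Equal 10% dropout leaves a gap of 34.0 − 30.6 = 3.4 points.

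**4. Direction.** The gap favours the active arm when r1·d1 exceeds r0·d0. With these ACR20 rates it reverses only if placebo dropout exceeds 0.67/0.33 = 2.03 times active dropout. At 5% active and 20% placebo, 0.6365 − 0.264 = 0.3725, so the as-observed difference is then 3.25 points too small.

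**5. DAS28, for comparison.** Assume a completer difference of 1.0, placebo improvement of 0.6, SD 1.2, a flat prior, 20 per arm now and 82 at the end, and 5% placebo dropout. Scoring stoppers as no change gives a difference of (1 − d1) × 1.6 − 0.95 × 0.6 = 0.87, 0.71 and 0.55 at 10%, 20% and 30% active dropout. By simulation, the chance of meeting the 1.0 rule at 80% is about 23% on observed data, against 14.1%, 6.6% and 2.9%. The chance of a futility flag is about 4-5% on observed data, against 7.5%, 15.5% and 27.9%. These figures measure the planned analysis against a no-change rule that appears nowhere in the plan. They do not measure an inconsistency between interim and final.

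**The case against.** A reader might infer that the whole interim decision ignores dropouts, counts them as failures later, and so flatters poorly tolerated doses. The documents do not support that.

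- The as-observed label covers only the descriptive summaries. The 1.0 and 0.6 rules rest on all available DAS28 data. The subjects not yet observed are most naturally those still to be enrolled or still to reach a visit. On known discontinuers the text is silent.
- Final DAS28 change is analysed under MAR, not as failure, so interim and final handling of DAS28 are broadly aligned.
- Early stoppers need not lack data. Protocol Table 5.1-2 requires an ET visit with joint counts, hsCRP and global assessments. Protocol 3.6 asks for continued follow-up after study drug stops. The fuller trigger wording requires completed assessments.
- Tolerability has its own route: AE and vital-sign review, a rule to drop arms with safety issues, and a Data Monitoring Committee. The cut-offs are given as examples, and the team may recommend rather than must act.

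All of this stands, and it confines the point to the binary summaries. There it does not remove the mismatch. An ET visit before Day 22 still yields no Week 4 response. Discontinuations by arm are not among the listed interim summaries. Stops for lack of efficacy or withdrawn consent can lower the final response rate without raising a safety issue.

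**Conclusion.** The point holds for the interim ACR and remission summaries. SAP 7.9 and SAP 8.5.1 treat early stoppers differently on the same endpoints, and the interim version feeds the futility call. An arm with more early stops looks better at the interim than it will under the final rule.

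The size cannot be fixed from the documents. Under the assumptions above, the as-observed ACR20 difference is larger by 3.4 points at equal 10% dropout and by about 12 points (34.0 − 22.25 = 11.75) at 20% against 5%. With about 20 subjects per arm, the latter means 4 stops against 1. Week 4 response rates may well differ from the Week 12 planning rates, and the gap scales with them. It shrinks if stoppers are assessed inside the window.

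The point does not extend to the DAS28 rules, and the documents do not establish that a poorly tolerated dose would be carried forward. This is a cheap improvement to the interim summaries, not a flaw in the final tests.

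**What to change.** 1. In SAP 7.9, make the main interim ACR and remission summaries use all treated subjects who reached the visit or stopped before it, with those who stopped scored as non-responders per SAP 8.5.1. Subjects still on treatment who have not reached the visit stay out of the denominator.
2. Keep the as-observed summaries as supportive, and tabulate discontinuations by arm and reason.
3. Put the same text in Protocol 8.5, which lacks the as-observed label. Reconcile the two versions of the trigger wording and of the role given to endpoints beyond DAS28.
4. Leave the 1.0 and 0.6 rules on the planned DAS28 analysis, and state how known discontinuers enter it. Add one sensitivity run with discontinuers at no improvement and future subjects simulated with the arm's observed stop rate. Making that run the basis of the rules would set the interim at odds with the final MAR analysis and raise the futility-flag rate.

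The cost is SAP and protocol wording, a little programming, and somewhat less favourable interim response rates. The protocol says recruitment was to stop on 30 November 2017, and the documents do not say whether the interim has been run. If it has, items 1, 2 and 4 become a documented re-summary.

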8 CONVENTIONS

8.1 Calculations of Key Measures

8.1.1 *Evaluation of ACR*

ACR 20, the American College of Rheumatology (ACR) definition of 20% improvement is based on a 20% improvement (compared to baseline (Day 1) values) in tender and swollen joint counts and 20% improvement in 3 of the remaining 5 core set measures (subject global assessment of pain, subject global assessment of disease activity, physician global assessment of disease activity, subject assessment of physical function and one acute phase reactant value (CRP)).

If ACR 20 response based on the criteria above, was not met, because no 20% improvement in tender and swollen joints, then the patient is an ACR20 non-responder.

If ACR 20 response, based on the criteria above was not met, because not 3 of the remaining 5 core set measures had 20 % improvement then the number of components with 20% or more improvement (for the 5 remaining core components) will be tabulated in relation to the number

of missing components (in the remaining 5 core components) prior to the final calculation of ACR 20. If the sum of the number of components with 20% or more improvement and the number of missing components is greater than or equal to 3, then ACR 20 will be set to missing as there is insufficient amount of data to determine the correct status, otherwise the patient is an ACR20 non responder.

Higher values for each component of the ACR composite variable indicate greater severity of disease. Improvement from baseline in a component of the ACR composite variable will be computed as the difference between the baseline value and the value at a given post-baseline visit. A positive value for improvement from baseline for an individual component indicates lesser severity of disease.

Percent improvement will be computed as the ratio of improvement from baseline to the baseline value times 100 for an endpoint:

$$\begin{aligned}\% \text{ Improvement} &= 100 * (\text{Improvement from Baseline}) / \text{Baseline Value} \\ &= 100 * (\text{Baseline Value} - \text{Post-baseline Value}) / \text{Baseline Value}.\end{aligned}$$

Based on the percent improvement from baseline in each of the ACR components, ACR 50 and ACR 70 will be similarly defined with 50% and 70% improvement, respectively.

The conventions for dealing with missing data, procedures or intra-articular injections of joints (has impact on tender and swollen joint counts), restricted medications and high dose of corticosteroids are provided in [Section 8.2, 8.3, 8.5.1](#).

8.1.2 *Evaluation of DAS28-CRP and DAS28-ESR*

The DAS used in this protocol is the DAS using the 28-count subsets of tender/painful joints and swollen joints, together with either CRP or erythrocyte sedimentation rate ESR, to derive the, DAS28-CRP, and DAS28-ESR, which are calculated using the following formulae, respectively:

$$\text{DAS28-CRP} = 0.56 * \text{sqrt}(\text{TJC28}) + 0.28 * \text{sqrt}(\text{SJC28}) + 0.36 * \text{ln}(\text{CRP}+1) + 0.014 * \text{GH} + 0.96.$$

$$\text{DAS28-ESR} = 0.56 * \text{sqrt}(\text{TJC28}) + 0.28 * \text{sqrt}(\text{SJC28}) + 0.70 * \text{ln}(\text{ESR}) + 0.014 * \text{GH}.$$

where TJC28 is number of painful joints out of 28 joints, SJC28 is number of swollen joints out of 28 joints, GH is the general health or patients' global assessment of disease activity on a 100 mm VAS, ln is the natural logarithm, ESR is in mm/hour, and CRP is in mg/L.

8.1.3 *Evaluation of CDAI*

Calculation of Clinical Disease Activity Index (CDAI) is the simple linear sum of the outcome parameters: tender joint count (TJC) and swollen joint count (SJC) based on a 28-joint assessment, patient global assessment of disease activity (PGA: VAS 0–10 cm), and physician global assessment of disease activity (EGA: VAS 0–10 cm):

$$\text{CDAI} = \text{TJC28} + \text{SJC28} + \text{PGA} + \text{EGA}.$$

CDAI Remission responder is defined as a CDAI score less than or equal to 2.8.

8.1.4 *Evaluation of SDAI and Boolean-based Remission*

Calculation of Simple Disease Activity Index (SDAI) is the simple linear sum of the outcome parameters: tender joint count (TJC) and swollen joint count (SJC) based on a 28-joint assessment, patient global assessment of disease activity (PGA: VAS 0–10 cm), physician global assessment of disease activity (EGA: VAS 0–10 cm) and C-reactive protein (CRP in mg/dL) as shown below:

$$\text{SDAI} = \text{TJC28} + \text{SJC28} + \text{PGA} + \text{EGA} + \text{CRP}.$$

SDAI Remission responder is defined as a SDAI score less than or equal 3.3.

Remission by Boolean-based definition: Subject must satisfy all of the followings:

$$\text{TJC28} \leq 1; \text{SJC28} \leq 1; \text{PGA} \leq 1; \text{CRP} \leq 1 \text{ mg/dL}$$

8.1.5 *Evaluation of HAQ Disability Index*

Scoring conventions for the Standard Disability Index of HAQ will be followed. The Standard disability index (HAQ DI) takes into account the subject's use of aids or devices or assistance in the scoring algorithm for a disability category. The score for each category is the single response within the category with the highest score. For each of the eight disability categories there is an AIDS OR DEVICES companion variable(s) that is used to record the type of assistance, if any, a subject uses for his/her usual activities. If aids or devices and/or assistance from another person are checked for a disability category, the score for this category is set to 2 (much difficulty), if the original score is 0 (no difficulty) or 1 (some difficulty). The HAQ DI is then calculated by summing the adjusted categories scores and dividing by the number of categories answered. The HAQ DI cannot be calculated if the patient does not have scores for at least 6 categories. Details of the HAQ DI scoring conventions are documented in “The Health Assessment Questionnaire”¹⁴.

A HAQ response for RA is defined as a subject with a reduction from baseline in HAQ DI of at least 0.22.

8.1.6 *Evaluation of FACIT-Fatigue*

The FACIT-Fatigue is a 13 item subject self-assessment tool that measures the subjects' usual daily activities over the past week. Responses of 'not at all', 'a little', 'somewhat', 'quite a bit', and 'very much' are available for each question, and correspond to scores of 0, 1, 2, 3, and 4, respectively for the item codes An5 and An7 and correspond to scores of 4, 3, 2, 1, 0 (reversal of response) for the other item codes.

The total score = (sum of scores) *13/ (number of items answered), resulting in a maximum of 52 and a minimum of 0. The total score cannot be calculated if the patient does not have answered at least 7 of the 13 items (more than 50 % of the items should be answered).

